3.1.2 Treatment Regimen

[REDACTED]

[REDACTED]

- [REDACTED]
- Placebo for 42 days (N = 8)

3.1.3 Dose Escalation

[REDACTED]

3.1.4 Management of Study Medication Related Toxicities

3.1.4.1 Tolerability

[REDACTED]

3.1.4.2 Hypoglycaemia

A hypoglycaemic event is considered severe if associated with severe cognitive impairment requiring external assistance for recovery, as defined by the American Diabetes Association. Spontaneous and clinically significant hypoglycaemia, defined as blood glucose < 3.0 mmol/L or 54 mg/dL with or without symptoms (hunger, dizziness, shaking, sweating, or irritability) (Skyder et al 2017), [REDACTED]

[REDACTED]. However, all subjects will be provided with a diary and a glucose meter and will be advised to check their capillary plasma glucose level if they have symptoms of hypoglycaemia or feel unwell, and will be expected to record the level in their diary. Local procedures for treatment and follow-up of any hypoglycaemic episode should be followed. Any blood glucose level of < 3.0 mmol/L (54 mg/dL) is considered

clinically significant hypoglycaemia and should be reported by investigators as an AE, regardless of whether or not subjects experience symptoms. Pharmacological treatments administered for hypoglycaemia, eg, dextrose/glucose tablets, glucagon etc, should be recorded in the electronic case report form (eCRF) as concomitant medications.

[figure not shown]
3.1.4.3 Hyperglycaemia

In the event of suspected persistent hyperglycaemia in a subject based on either symptoms of hyperglycaemia (eg, thirst, polyuria, blurred vision) or capillary plasma glucose readings (eg, 3 readings > 14 mmol/L [260 mg/dL] within 1 week), the investigator should perform additional fasting blood glucose level tests as necessary. If 2 or more laboratory plasma fasting glucose levels of > 14 mmol/L (260 mg/dL) more than 3 days apart are detected, the investigator should consider rescue therapy following discussion with the medical monitor.

In the unlikely event that a subject is unwell and severe persistent hyperglycaemia (eg, fasting glucose > 14 mmol/L [260 mg/dL]) is suspected by the investigator, the subject should be advised to monitor capillary plasma glucose levels up to 5 times per day and rescue therapy should be administered within a 24- to 48-hour time frame if required.

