4.1.6 Discontinuation of Investigational Product

An individual subject will not receive any further investigational product if any of the following occur in the subject in question:

- 1 Withdrawal of consent from further treatment with investigational product
- 2 Lost to follow-up
- 3 An AE that, in the opinion of the investigator or the sponsor, contraindicates further dosing: specific examples include:
 - Dose-limiting symptoms with respect to GI tolerability and in particular if a subject requires intravenous fluids for more than 48 hours to treat volume depletion

secondary to nausea and vomiting, even after measures are taken to reduce the risk of vomiting, after discussion with the medical monitor

- Any subject where Hy's law criteria on liver function tests is met: AST or ALT $\geq 3 \times$ ULN **together with** total bilirubin $\geq 2 \times$ ULN
 - Any subject who develops a life-threatening arrhythmia including sustained ventricular tachycardia, ventricular fibrillation or new ECG changes of second or third-degree heart block
 - Subjects with persistent fasting glucose level of > 260 mg/dL (14.4 mmol/L) despite a maximum tolerated dose of rescue therapy to enable optimisation of the subject's glycaemic control
- 4 Subject noncompliance that, in the opinion of the investigator or sponsor, warrants withdrawal (eg, refusal to adhere to scheduled visits)
 - 5 Pregnancy in a female subject

Subjects who are permanently discontinued from receiving investigational product will be followed for protocol-specified assessments including follow-up of any AEs unless consent is withdrawn from further study participation (Section 4.1.5), the subject is lost to follow-up, the subject starts alternative treatment, or the subject is enrolled in another clinical study.

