4.3.5.1 Glucose Meter Measured Capillary Plasma Glucose Readings

At the start of the study, each subject will be issued a standardised glucose meter, testing strips, and a diary. Subjects will be requested to record a capillary glucose reading pre-breakfast every 72 hours and will also be encouraged to perform finger-prick tests if they feel unwell, and in particular if they feel the symptoms may be due to hypoglycaemia for the duration of the study (Section 3.1.4.2). If the investigator/site staff feel that a subject could be experiencing hypo- or hyperglycaemia, capillary plasma glucose should be tested with a standardised glucose meter. Capillary plasma glucose levels of < 3 mmol/L (54 mg/dL) should be recorded as an AE regardless of whether the subject has symptoms or not. Readings taken by the subject at home will be recorded electronically or in a paper diary.

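### The hyperglycaemia threshold in Protocol 3.1.4.3 is given three times as 14 mmol/L (260 mg/dL), but 14 mmol/L is 252 mg/dL and 260 mg/dL is 14.4 mmol/L

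*Protocol*

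**What the plan says.** Protocol 3.1.4.3 (Hyperglycaemia) uses one threshold, in two units, for three purposes:

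- Home or site meter readings that lead to further fasting tests: "capillary plasma glucose readings (eg, 3 readings > 14 mmol/L [260 mg/dL] within 1 week".
- Laboratory values at which rescue is to be considered with the medical monitor: "If 2 or more laboratory plasma fasting glucose levels of > 14 mmol/L (260 mg/dL) more than 3 days apart are detected".
- The unwell subject, who is to check glucose up to 5 times a day and receive rescue within 24 to 48 hours if required: "severe persistent hyperglycaemia (eg, fasting glucose > 14 mmol/L [260 mg/dL]) is suspected by the investigator".

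Two other places in the protocol convert glucose between the units. Section 3.1.4.2 (Hypoglycaemia) has "Any blood glucose level of < 3.0 mmol/L (54 mg/dL) is considered" clinically significant. Section 4.1.6 (Discontinuation of Investigational Product) has "Subjects with persistent fasting glucose level of > 260 mg/dL (14.4 mmol/L) despite a maximum tolerated dose of rescue therapy" as a reason to stop dosing.

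**The concern.** Section 3.1.4.3 equates 260 mg/dL with 14 mmol/L, whereas section 4.1.6 equates the same 260 mg/dL with 14.4 mmol/L. Both cannot be right, and the hypoglycaemia pair shows that the error is in 3.1.4.3.

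The limits are strict inequalities that guide safety decisions. Read in mmol/L they prompt action earlier; read in mg/dL, later. The mismatch also obscures how rescue and discontinuation relate. In mg/dL the two steps share one limit (260). In mmol/L rescue is considered 0.4 mmol/L below the discontinuation limit (14 against 14.4). A reader cannot tell which was meant.

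Raised glucose is a foreseeable event in this trial. Subjects on dual therapy stop their non-metformin agent 28 days before Visit 4, all subjects take placebo for 16 days, and the 8 placebo subjects continue on it for another 42.

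**Working it through.** **Inputs**

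| Source | mmol/L | mg/dL | Implied mg/dL per mmol/L |
|---|---|---|---|
| Protocol 3.1.4.2, hypoglycaemia | 3.0 | 54 | 54 / 3.0 = 18.00 |
| Protocol 4.1.6, discontinuation | 14.4 | 260 | 260 / 14.4 = 18.06 |
| Protocol 3.1.4.3, testing and rescue (three times) | 14 | 260 | 260 / 14 = 18.57 |

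The first two factors agree to within rounding. The third agrees with neither.

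**Attempt to reproduce the stated pair.** Formula: mg/dL = mmol/L × factor.

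- Factor 18.00: 14 × 18.00 = 252.0 mg/dL, and 260 / 18.00 = 14.44 mmol/L.
- Factor 18.06 (260 / 14.4, unrounded): 14 × 260 / 14.4 = 252.8 mg/dL, and 260 mg/dL = 14.40 mmol/L.

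Neither factor gives 260 mg/dL for 14 mmol/L, so the pair is not reproduced.

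**Check of section 4.1.6.** 14.4 × 18 = 259.2 mg/dL, and 260 / 18 = 14.44, which rounds to 14.4. That pair is correct to rounding.

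**Size of the gap (factor 18).** 260 − 252 = 8 mg/dL. 8 / 18 = 0.44 mmol/L. 8 / 252 = 3.2%.

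**When the two units disagree.** A value of 14.2 mmol/L is 14.2 × 18 = 255.6 mg/dL, so it is above 14 mmol/L but not above 260 mg/dL. For a trigger that needs several readings, the units disagree when enough readings exceed 14.0 mmol/L but too few of them also exceed about 14.4 mmol/L.

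- *Capillary trigger, 3 readings in a week.* Section 4.3.5.1 states: "Subjects will be requested to record a capillary glucose reading pre-breakfast every 72 hours". A 7-day window is 168 hours, so scheduled readings fall at 0, 72 and 144 hours at most, which is three. On that schedule alone all three are needed. If all exceed 14.0 mmol/L, a single one in the band means the trigger is met in mmol/L and not in mg/dL.
- *Laboratory trigger, 2 or more fasting values.* The same holds when exactly two values are available, both exceed 14.0 mmol/L, and at least one lies in the band.

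**The case against.** Nobody can defend the pair as a conversion, so the case on the other side concerns weight.

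- **It is probably rounding.** 260 / 18 = 14.44, which is 14 as a whole number. That is a likely origin, but it does not make the two strict limits the same rule, and section 4.1.6 keeps the decimal.
- **Two of the three places are only examples.** The capillary readings and the unwell-subject level are introduced as illustrations, and symptoms alone can start the work-up. This stands. Only the laboratory criterion is a firm count, limit and interval, and even there the investigator is asked to consider rescue after discussion, so no action is automatic.
- **One UK site, with mmol/L written first.** A reader who follows the leading unit gets a single value, 14 mmol/L, which is also the earlier trigger. This weakens the practical concern but does not remove it. Section 4.1.6 puts mg/dL first, and the documents do not say which unit the meters or laboratory reports use.
- **The disagreement needs a narrow set of readings.** Entry requires HbA1c of 8.0% or lower. Extra tests when a subject feels unwell could add readings above 14.4 mmol/L and so settle the matter. This stands too: disagreement is possible, but the documents give no basis for saying how often it would occur.

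These points keep the concern small. None of them makes the figures agree.

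**Conclusion.** The concern holds. The pair in section 3.1.4.3 is wrong in all three places, on the evidence of the protocol's own two other glucose conversions; no outside figure is needed. The error is 8 mg/dL, or 0.44 mmol/L, about 3.2% of the threshold. The range of factors implied by the protocol (18.00 to 18.06) does not change the conclusion: 14 mmol/L is 252.0 to 252.8 mg/dL, and 260 mg/dL is 14.40 to 14.44 mmol/L.

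It is a minor point. It affects the timing of discretionary safety steps for values inside a narrow band, and no efficacy result. The statement that one reading in the band can decide the capillary trigger assumes scheduled readings only. The discontinuation rule in section 4.1.6 is a separate, later step with a correct pair and is not in question.

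**What to change.** In all three places in Protocol 3.1.4.3, write one consistent pair:

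- 14.4 mmol/L (260 mg/dL), which matches section 4.1.6; or
- 14 mmol/L (252 mg/dL), if testing and rescue are meant to start at a lower level than the discontinuation limit.

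The choice is clinical and belongs to the sponsor's clinical team. Section 4.1.6 needs no change. The cost is a wording correction at three places in one section, with no effect on procedures, analysis or sample size.

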3.2 Rationale for Dose, Population, and Endpoints

MEDI0382 is being developed for the treatment of T2DM and obesity.

3.2.1 Dose Rationale

[REDACTED]

[REDACTED] (Table 4).

Table 4 Proposed Study Dose and Predicted Safety Margin Based on Safety Data from the Cynomolgus Monkey

[REDACTED]	[REDACTED]		[REDACTED]	
	[REDACTED]	[REDACTED]	[REDACTED]	[REDACTED]
[REDACTED]	[REDACTED]	[REDACTED]	[REDACTED]	[REDACTED]

[REDACTED]

3.2.2 Rationale for Study Population

Subjects aged ≥ 30 and ≤ 75 years, with BMI > 28 and ≤ 40 kg/m² will be included in the study population to balance recruitment potential with projected variability in EE measurements. Conflicting reports exist with respect to the impact of obesity on EE (Carneiro et al 2016) and subjects with T2DM have differing REE and AEE, and this may be influenced by glycaemic control (Caron et al 2016). In view of this, subjects without poor glycaemic control (HbA1c $\leq 8.0\%$) using metformin, dipeptidyl peptidase-4 (DPP4) inhibitors, sodium-glucose co-transporter inhibitors (SGLT2i), sulfonylurea, or glitinide will be enrolled; if they are on dual therapy, the non-metformin therapy will be washed out 4 weeks prior to dosing of MEDI0382 (Visit 4). In addition, subjects that partake in high intensity exercise (and likely have a high BMI due to excess muscle bulk) will be excluded.

3.2.3 Rationale for Endpoint(s)

3.2.3.1 Primary Endpoint

[REDACTED]

[REDACTED] eight loss is an established surrogate measure of energy balance and therefore percentage change in body weight will provide an overview of net energy balance versus placebo across the course of 42 days of MEDI0382 dosing (Hill et al 2014).

3.2.3.2 Secondary Endpoints

Energy Intake

Given that prior studies undertaken with GLP-1 and glucagon receptor-agonists and oxm have revealed significant effects on energy intake, it is likely that MEDI0382 influences energy intake. Energy intake may be measured in a more robust way than self-report through single-blind assessment of ad libitum meal consumption.

Energy Expenditure

Given the findings of prior research describing an increase in differential components of EE it will be important to determine the effect of MEDI0382 on TEE, AEE, and REE (Section 1.2). Gold standard methodology including whole room indirect calorimetry and DLW will be used in addition to an activity monitor to obtain estimates of EE as secondary and exploratory endpoints during the study. As fluctuations in weight and fat mass may influence estimates of EE, [REDACTED] and all measurements will be adjusted for total body fat mass as measured by dual X-ray absorptiometry (DXA) scanning. In addition, subjects will be asked to abstain from caffeinated drinks for at least 24 hours prior to measurements as caffeine may increase EE and dietary advice will be given to ensure subjects have a neutral energy balance prior to whole calorimetry assessments.

Body Weight and Composition

In addition to the primary endpoint of percentage change in body weight, absolute change in body weight will also provide an overview of net energy balance versus placebo across the course of 42 days of MEDI0382 dosing.

[REDACTED]

Glucose Homeostasis

[REDACTED]

Safety and Tolerability

As MEDI0382 remains under development, safety and tolerability will be assessed throughout this study.

Standard safety endpoints including vital signs, safety laboratory analysis, treatment-emergent adverse events (TEAEs), treatment-emergent serious adverse events (TESAEs), and electrocardiograms (ECGs) will be assessed during treatment and follow-up.

[REDACTED]

Immunogenicity

[REDACTED]

3.2.3.3 Exploratory Endpoints

MEDI0382 Exposure

[REDACTED]

[REDACTED]

[REDACTED]

[REDACTED]

[REDACTED]

[REDACTED]

[REDACTED]

[REDACTED]

[REDACTED]

[REDACTED]

[REDACTED] **Satiety**

[REDACTED]

4 MATERIALS AND METHODS

4.1 Subjects

4.1.1 Number of Subjects

Enrolment of approximately 24 subjects is planned.

4.1.2 Inclusion Criteria

Subjects must meet all of the following criteria:

- 1 Subjects aged ≥ 30 and ≤ 75 years at screening
- 2 Provision of signed and dated written informed consent (except for consent for genetic and non-genetic research and additional optional assessments) prior to any protocol-related procedures
- 3 Body Mass Index > 28 and ≤ 40 kg/m² at screening
- 4 Glycated haemoglobin (HbA1c) $\leq 8.0\%$ at screening
- 5 Diagnosed with T2DM with glucose control managed with metformin, with or without a DPPIV inhibitor, SGLT2i, sulfonylurea, or glitinide, where no significant dose change (increase or decrease $> 50\%$) has occurred in the 3 months prior to screening; if the

subject is on dual therapy, a 4-week washout of the non-metformin therapy (DPPIV inhibitor, SGLT2i, sulfonylurea, or glitinide) will be required prior to Visit 4

- 6 Female subjects of childbearing potential must have a negative pregnancy test at screening and randomisation, and must not be lactating
- 7 Female subjects of childbearing potential who are sexually active with a non-sterilised male partner must be using at least one highly effective method of contraception (see Section 10.2 for definition of females of childbearing potential and for a description of highly effective methods of contraception) from screening and must agree to continue using such precautions up until 4 weeks after the last dose of investigational product

4.1.3 Exclusion Criteria

Any of the following would exclude the subject from participation in the study:

- 1 History of, or any existing condition(s) that, in the opinion of the investigator, would interfere with evaluation of the investigational product, put the subject at risk, influence the subject's ability to participate or affect the interpretation of the results of the study and/or any subject unable or unwilling to follow study procedures
- 2 Any subject with a cardiac pacemaker or implanted/portable electronic device
- 3 Any subject who has received another investigational product as part of a clinical study or a GLP-1 analogue-containing preparation within the last 30 days or 5 half-lives of the drug (whichever is longer) at the time of screening (Visit 1)
- 4 Any subject who has received any of the following medications within the specified time frame prior to Visit 2: herbal preparations or drugs licensed for control of body weight or appetite (eg, orlistat, bupropion, naltrexone, phentermine-topiramate, phentermine, lorcaserin, opiates, domperidone, metoclopramide, or other drugs known to alter gastric emptying)
- 5 Concurrent participation in another study with an investigational product and prior randomisation in this study is prohibited
- 6 Severe allergy/hypersensitivity to any of the proposed study treatments, excipients, or standardised meals
- 7 Symptoms of acutely decompensated blood glucose control (eg, thirst, polyuria, weight loss), a history of type 1 diabetes mellitus or diabetic ketoacidosis, or if the subject has been treated with daily SC insulin within 90 days prior to screening
- 8 Abnormal thyroid stimulating hormone (TSH) level of < 0.03 mIU/L or > 10 mIU/L confirmed on two consecutive tests
- 9 Regularly engage in high intensity exercise at least three times per week or have done so in the prior three months
- 10 Clinically significant inflammatory bowel disease, gastroparesis or other severe disease or surgery affecting the upper GI tract (including weight-reducing surgery and procedures)

which may affect gastric emptying or could affect the interpretation of safety and tolerability data

- 11 Acute or chronic pancreatitis with or without amylase > 1000 IU/L and/or lipase > 600 IU/L at screening
- 12 Significant hepatic disease (except for nonalcoholic steatohepatitis or nonalcoholic fatty liver disease without portal hypertension or cirrhosis) and/or subjects with any of the following results at screening:
 - (a) Aspartate transaminase (AST) $\geq 3 \times$ upper limit of normal (ULN)
 - (b) Alanine transaminase (ALT) $\geq 3 \times$ ULN
 - (c) Total bilirubin $\geq 2 \times$ ULN
- 13 Impaired renal function defined as estimated glomerular filtration rate (eGFR) < 45 mL/minute/1.73 m² at screening (GFR estimated according to the Chronic Kidney Disease-Epidemiology Collaboration (CKD-EPI) or the Modification of Diet in Renal Disease (MDRD) using MDRD Study Equation isotope dilution mass spectrometry-traceable [SI units])
- 14 Poorly controlled hypertension defined as:
 - (a) Systolic BP > 180 mm Hg
 - (b) Diastolic BP or > 100 mm Hg

After 10 minutes of supine rest and confirmed by repeated measurement at screening. Subjects who fail BP screening criteria may be considered for 24-hour ambulatory blood pressure monitoring at the discretion of the investigator. Subjects who maintain a mean 24-hour BP $\leq 180/100$ mmHg with a preserved nocturnal dip of $> 15\%$ will be considered eligible

- 15 Unstable angina pectoris, myocardial infarction, transient ischemic attack or stroke within 3 months prior to screening, or subjects who have undergone percutaneous coronary intervention or a coronary artery bypass graft within the past 6 months or who are due to undergo these procedures at the time of screening
- 16 Severe congestive heart failure (New York Heart Association Class III or IV)
- 17 Basal calcitonin level > 50 ng/L at screening or history/family history of medullary thyroid carcinoma or multiple endocrine neoplasia
- 18 History of neoplastic disease within 5 years prior to screening, except for adequately treated basal cell, squamous cell skin cancer, or in situ cervical cancer
- 19 Any positive results for serum hepatitis B surface antigen (HBsAg), hepatitis C antibody and human immunodeficiency virus (HIV) antibody
- 20 Substance dependence or history of alcohol abuse and/or excess alcohol intake

- 21 Involvement of any AstraZeneca, MedImmune, contract research organization (CRO), or National Institute for Health Research/Wellcome Trust Cambridge Clinical Research Facility employee or their close relatives

4.1.4 Subject Enrolment and Randomisation

Study participation begins (ie, a subject is 'enrolled') once written informed consent is obtained. Once informed consent is obtained, a subject identification (SID) number will be assigned by an interactive voice/web response system (IXRS). The SID number will be assigned prior to the beginning of screening evaluations to assess study eligibility (inclusion/exclusion) criteria. The SID number will be used to identify the subject during the screening process and throughout study participation, if applicable.

A master log of all consented subjects will be maintained at the site and will document all screening failures (ie, subjects who are consented but do not meet study eligibility criteria and/or are not randomised), including the reason(s) for screening failure.

Subjects who fail to meet the eligibility criteria (ie, screening failures) should not be randomised or receive investigational product. Subjects may be rescreened once and receive a new SID number if, in the opinion of the investigator, there is a reason to believe they may be eligible.

Subjects who are enrolled, but subsequently found not to meet all the eligibility criteria must not be randomised or receive investigational product, and must be withdrawn from the study.

4.1.5 Withdrawal from the Study

Subjects are free to withdraw their consent to participate in the study (investigational product and assessments) at any time, without prejudice to further treatment. Subjects who withdraw consent will be asked about the reason(s) and the presence of any AEs. After consent is withdrawn, no further study visits or data collection should take place.

4.1.6 Discontinuation of Investigational Product

An individual subject will not receive any further investigational product if any of the following occur in the subject in question:

- 1 Withdrawal of consent from further treatment with investigational product
- 2 Lost to follow-up
- 3 An AE that, in the opinion of the investigator or the sponsor, contraindicates further dosing: specific examples include:
 - Dose-limiting symptoms with respect to GI tolerability and in particular if a subject requires intravenous fluids for more than 48 hours to treat volume depletion

secondary to nausea and vomiting, even after measures are taken to reduce the risk of vomiting, after discussion with the medical monitor

- Any subject where Hy's law criteria on liver function tests is met: AST or ALT $\geq 3 \times$ ULN **together with** total bilirubin $\geq 2 \times$ ULN
 - Any subject who develops a life-threatening arrhythmia including sustained ventricular tachycardia, ventricular fibrillation or new ECG changes of second or third-degree heart block
 - Subjects with persistent fasting glucose level of > 260 mg/dL (14.4 mmol/L) despite a maximum tolerated dose of rescue therapy to enable optimisation of the subject's glycaemic control
- 4 Subject noncompliance that, in the opinion of the investigator or sponsor, warrants withdrawal (eg, refusal to adhere to scheduled visits)
 - 5 Pregnancy in a female subject

Subjects who are permanently discontinued from receiving investigational product will be followed for protocol-specified assessments including follow-up of any AEs unless consent is withdrawn from further study participation (Section 4.1.5), the subject is lost to follow-up, the subject starts alternative treatment, or the subject is enrolled in another clinical study.

